7.1 Food Allergy Episodes

In order to report the occurrence of a safety event associated with accidental food ingestion, subjects will be instructed to contact the site study coordinator or investigator for any adverse event. The subject may be asked to return to the site. A Food Allergy Episode form will be completed for each of these events in addition to events where consumption of egg without a reaction occurs. If the accidental food ingestion safety event meets the definition of a serious adverse event, as defined below, the AE/SAE form will be completed as well.

7.2 Definitions

All safety events observed under this protocol are reported through the data system from the time of the first study procedure until the 2 year sustained unresponsiveness OFC (Visit 08). Additionally, safety events will be collected until the 6 month in clinic follow-up visit for those subjects who pass the 2-year sustained unresponsiveness challenge. Safety events outside of food allergy episodes will not be collected during the annual phone follow-up period. Safety events related to accidental food exposure are recorded on a Food Allergy Episode form and are not reported on an adverse event form unless the event is considered a serious adverse event, as defined below. Any systemic allergic symptoms due to dosing will be recorded on a Study Product Administration form. If the event meets the definition of a serious adverse event, it will also be recorded on an adverse event (AE)/serious adverse event (SAE) form. Prick skin test and food challenge reactions that occur in the clinic are captured on study specific forms and are not reported on an adverse event form unless the event is considered a serious adverse event, as defined below. All serious adverse events are reported on the AE/SAE form set in addition to the Prick Skin form or an Oral Food Challenge form if the event occurred during one of these procedures. All other safety events that occur throughout the study are reported on the AE/SAE form set.

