7.2.1 Adverse Event (AE) or Medical Event

Any untoward or unfavorable medical occurrence associated with the subject's participation in the research, whether or not considered related to the subject's participation in the research (modified from the definition of adverse events in the 1996 International Conference on Harmonization E-6 Guidelines for Good Clinical Practice) (from OHRP "Guidance on

Reviewing and Reporting Unanticipated Problems Involving Risks to Subjects or Others and Adverse Events (1/15/07)" http://www.hhs.gov/ohrp/policy/advevntguid.html#Q2).

An AE will be followed until it resolves or until 30 days after a participant terminates from the study, whichever comes first. Any change in clinical status, ECGs, routine labs, x-rays, physical examinations, etc., that is considered clinically significant by the study investigator is considered an AE. For the purposes of this protocol, consider a pregnancy an adverse event and follow the event until resolution of the pregnancy.

Suspected adverse reaction (SAR) is any adverse event for which there is a reasonable possibility that the drug caused the adverse event. For the purposes of safety reporting, 'reasonable possibility' means there is evidence to suggest a causal relationship between the drug and the adverse reaction. A suspected adverse reaction implies a lesser degree of certainty about causality than adverse reaction, which means any adverse event caused by a drug (21 CFR 312.32(a)).

Adverse reaction is any adverse event caused by the drug. Adverse reactions are a subset of all suspected adverse reactions for which there is reason to conclude that the drug caused the event.

7.2.2 Serious Events (Serious Adverse Events, Serious Suspected Adverse Reactions or Serious Adverse Reactions)

An AE or SAR is considered "serious" if, in the view of either the investigator or DAIT/NIAID/NIH it results in any of the following outcomes (21 CFR 312.32(a)):

- 1. Death: A death that occurs during the study or that comes to the attention of the investigator during the protocol-defined follow-up period must be reported whether it is considered treatment related or not.
- 2. A life-threatening event: An AE or SAR is considered "life-threatening" if, in the view of either the investigator or DAIT/NIAID/NIH, its occurrence places the subject at immediate risk of death. It does not include an AE or SAR that, had it occurred in a more severe form, might have caused death.

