7.4 Adverse Events Collection Procedures

Adverse events will be evaluated from the onset of the event until the time the event is resolved or medically stable, or until 30 days after the subject completes study treatment, whichever comes first.

AEs may be discovered through any of these methods:

- Observing the subject
- Questioning the subject, which should be done in an objective manner
- · Receiving an unsolicited complaint from the subject
- Review of medical records/source documents
- Review of home dosing symptom logs (provided to record symptoms between visits)

7.4.1 Recording and Reporting Procedures

Throughout the study, the investigator will record all AEs on the appropriate eCRF regardless of their severity or relation to study participation. A multi-page adverse event form will be used allowing all adverse events to be submitted through a single reporting mechanism. Serious adverse events will require additional information reported on additional pages within the EMMES AdvantageEDCSM system. Source documents can be scanned and attached to the adverse event form as well. The investigator will treat subjects experiencing adverse events appropriately and observe them at suitable intervals until their symptoms resolve or their status stabilizes.

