9.3 Sample Size and Power Calculations

The sample size target for the randomized portion of the study is 96 individuals with 1:1 random assignment to Baked Egg and Egg OIT. The sample size was selected to determine whether a

difference exists between the treatment groups in the primary endpoint rate for the sustained unresponsiveness-focused portion of the study. Specifically, the sample was designed to have 85% power to detect with a two-sided 5% level test, a difference between a 40% and 70% sustained unresponsiveness rate. While a small dropout rate may occur, we will use all randomized cases who initiate treatment in the intent-to-treat analysis of the primary endpoint; failures associated with noncompliance are include in the denominator for event rates above.

This sample size is sufficient to address the secondary endpoint of the desensitization components of the study for event rate differences of comparable size.

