9.2 Deaths, Serious Adverse Events and other Significant Adverse Events

The proportion of participants experiencing a SAE will be estimated within each group. Pairwise comparisons between treatment groups will be performed using Barnard's exact unconditional test at the two-sided 5% level. If multiple SAEs are observed within a participant, alternate methods to account for the multiple events will be considered. If SAEs are infrequent (e.g. 1 or 2 events throughout the study), then hypothesis testing may not be performed. SAEs will also be described by relatedness to study product or procedure.

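### The SAE window ends later for children who achieve sustained unresponsiveness, so the crude SAE comparison is slightly tilted against the more effective arm

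*Protocol*

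**What the plan says.** Protocol 7.2 collects safety events "from the time of the first study procedure until the 2 year sustained unresponsiveness OFC (Visit 08"). It then extends the period for one subgroup: "safety events will be collected until the 6 month in clinic follow-up visit for those subjects who pass the 2-year sustained unresponsiveness challenge". Appendix 1.D confirms that the 3-month and 6-month follow-up contacts are only for children who pass the SU challenge. The footnotes to Appendices 1.A and 1.B say that Visit 08 (weeks 112-114) is held only if the Year 2 on-therapy challenge (Visit 07, week 104) is passed. Section 7.2 gives no end date for children who have no Visit 08.

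The SAE endpoint in SAP 3.2 covers all SAEs during the study, and SAP 9 calls it the primary safety endpoint. Under SAP 9.2, "The proportion of participants experiencing a SAE will be estimated within each group", and groups are compared pairwise by Barnard's test at the two-sided 5% level. No start date, cutoff or person-time is given. SAP 6.3 limits the safety population to treated participants and lets it vary by time period, but sets no period for SAEs. The treatment-emergent restriction appears only for other adverse events (SAP 9.1.2.3).

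**The concern.** Three groups of children are observed for different lengths of time, and the primary endpoint decides which group a child is in:

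- Children who fail the Year 2 challenge, or never take it, have no Visit 08 and no stated end of collection.
- Children who pass at Year 2 but fail the SU challenge are observed to Visit 08.
- Children who achieve SU are observed for about six months more.

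The extra time also differs in kind. Visit 08 adds another 7444 mg challenge, and after it the SU successes are advised to eat egg regularly (Protocol 6.4, Two Year OFC). Both features give more opportunity to record an SAE in the arm with more successes. With equal underlying risk, a crude proportion would still tend to be higher in that arm.

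The start of the window raises a second, narrower issue. Collection begins with the first study procedure, so an SAE in a screening or baseline challenge counts. Children in the eOIT-Randomized group have two challenges before treatment (baked egg, then egg). Those in eOIT-Assigned have one, and reacting to it is what put them in that group.

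**Working it through.** **The plan's own figure.** Protocol 9.3 states "85% power to detect with a two-sided 5% level test, a difference between a 40% and 70% sustained unresponsiveness rate", with 96 children randomised 1:1. With pooled rate 0.55:

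n per arm = [1.960 × √(2 × 0.55 × 0.45) + 1.036 × √(0.40 × 0.60 + 0.70 × 0.30)]² / 0.30² = 47.8, rounded up to 48, so 96 in all. Power at 48 per arm is 0.851. The stated figure is reproduced. The plan gives no design figure for the SAE comparison.

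**Inputs for the window.**
- SU rates 40% and 70% (Protocol 9.3).
- Visit 07 at week 104; Visit 08 at weeks 112-114, taken as week 113 (Appendices 1.A and 1.B).
- The 6-month visit, taken as 26 weeks after Visit 08. An SU passer is then observed to week 113 + 26 = 139.
- Everyone else: either week 113 or week 104. These are bounds. The text is silent for children without Visit 08, and children who fail the SU challenge are observed to Visit 08.
- Assumption: nobody leaves before week 104.

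**Mean window per arm** = p(SU) × 139 + (1 − p) × other window.

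| Others observed to | Baked Egg | Egg OIT | Difference | Ratio |
|---|---|---|---|---|
| week 113 | 0.40 × 139 + 0.60 × 113 = 123.4 | 0.70 × 139 + 0.30 × 113 = 131.2 | 7.8 weeks | 1.06 |
| week 104 | 0.40 × 139 + 0.60 × 104 = 118.0 | 0.70 × 139 + 0.30 × 104 = 128.5 | 10.5 weeks | 1.09 |

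The difference is the SU difference times the gap in window (26 or 35 weeks). Each 10 points of SU difference therefore adds 2.6 to 3.5 weeks.

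**Effect on the SAE proportion.** The documents give no SAE rate, so I assume a 104-week risk r, the same in both arms, with constant hazard λ = −ln(1 − r)/104. The proportion with an SAE over t weeks is f(t) = 1 − exp(−λt). The spurious difference is (0.70 − 0.40) × [f(139) − f(other window)].

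Example at r = 5%: f(139) = 6.63%, f(113) = 5.42%, f(104) = 5.00%. This gives 0.30 × 1.21 = 0.36 points, or 0.30 × 1.63 = 0.49 points.

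| Assumed 104-week risk | Spurious excess on Egg OIT (percentage points) |
|---|---|
| 2% | 0.15 to 0.20 |
| 5% | 0.36 to 0.49 |
| 10% | 0.70 to 0.94 |
| 20% | 1.28 to 1.74 |

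If the hazard were three times higher in the 26 weeks after Visit 08 (an assumption, standing for SAEs clustering when egg is introduced), the excess would be 1.1 to 1.2 points at 5% and 2.0 to 2.3 points at 10%.

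**Scale.** At 48 per arm, 0.94 points is 48 × 0.0094 = 0.45 of a child. With the constant hazard, the false-positive rate rises by at most about 0.5 points, using the uncorrected chi-square as a stand-in for Barnard's test.

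**With a common window to Week 104**, the planned windows are equal and the expected difference under equal hazards is zero.

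**The case against.** The case on the other side has several sound parts.

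- **Rarity.** Protocol 2.1 says that few SAEs and a small sample may limit this comparison, and SAP 9.2 allows the test to be dropped if SAEs are infrequent. That stands, and it is part of why the size is modest. It does not set a window for the case in which a test is run.
- **Relatedness.** SAP 9.2 will describe SAEs by relation to product or procedure, so challenge reactions can be told apart. That helps in reading the table but leaves the tested proportion unchanged.
- **Food reactions in other children.** Protocol 7.2 goes on collecting food allergy episodes during the annual calls to all subjects, and 7.1 sends a serious accidental-ingestion event to the SAE form. Serious food reactions are therefore not sought only among SU successes, although yearly recall is weaker than a clinic visit.
- **Legitimate events.** SAEs at Visit 08, or after egg is introduced, can fairly be read as consequences of treatment. They should not disappear from the endpoint, and the fix keeps them.

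A reader might also infer three stronger points that the documents do not support:

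- *Pre-treatment challenges bias the randomised comparison.* Both challenges precede randomisation (Protocol 6.4) and are the same for both arms. They add noise, not bias, to Baked Egg vs eOIT-Randomized. Only the comparison with eOIT-Assigned can be distorted, and that one is not randomised.
- *Collection stops at Month 24 for children who fail at Year 2.* The text does not say so. Section 4.3.2 keeps children who stop treatment in the study until normal termination. The defect is the missing end date.
- *Sections 7.2.1 and 7.4 cut off SAEs before Visit 08.* Section 7.2.1 says "An AE will be followed until it resolves or until 30 days after a participant terminates from the study, whichever comes first"; 7.4 says "until 30 days after the subject completes study treatment, whichever comes first". Both govern how long an event that has begun is followed. Capture is set by 7.2, which names Visit 08. The mismatch is real but minor: dosing ends at week 104, so the 7.4 limit falls near week 108 (104 + 30/7 = 108.3), before Visit 08.

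**Conclusion.** The point holds for the end of the window. As written, SAE observation time depends on the primary outcome, and nothing in the SAP equalises it. At the design SU rates the mean planned window is about 6% to 9% longer on Egg OIT. The resulting bias is about 0.15 to 0.94 percentage points for assumed SAE risks of 2% to 10%, and more if SAEs cluster when egg is introduced.

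These figures rest on the design SU rates, an assumed SAE risk that is equal in both arms, a constant hazard, and no early withdrawal. Withdrawals would shorten some windows, and unequal withdrawal could widen or narrow the gap. If the SU rates turned out equal, this difference in planned windows between the arms would largely vanish.

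A reader might conclude that the safety comparison cannot be trusted. The numbers do not support that. This is a gap in definition that should be closed, not a threat to the trial's main conclusion. With few SAEs, though, one or two late events in SU successes could change how the table reads. For eOIT-Randomized vs eOIT-Assigned, the pre-treatment challenges are a further source of distortion, because the groups have two and one of them.

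**What to change.** 1. In SAP 9.2, base the between-group test on SAEs with onset from first study dose to Week 104, in calendar time, for every treated child whether or not still on treatment. Say how a Visit 07 challenge held late is counted, since Protocol 6.9 allows two weeks either side.
2. Keep the all-study proportion with an SAE as a descriptive table, with an exposure-adjusted rate beside it. The rate also addresses shorter observation after withdrawal, which a fixed cutoff alone does not.
3. List pre-treatment SAEs and those after Week 104 separately, by group.
4. State in Protocol 7.2 when safety collection ends for children with no Visit 08.
5. As a separate minor matter, reconcile the follow-up limits in 7.2.1 and 7.4.

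The cost is some wording, an extra table and the listings. The drawback is that a few late events, including any at Visit 08, move from the test to the description. No SAE is lost from reporting.

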7.2.1 Adverse Event (AE) or Medical Event

Any untoward or unfavorable medical occurrence associated with the subject's participation in the research, whether or not considered related to the subject's participation in the research (modified from the definition of adverse events in the 1996 International Conference on Harmonization E-6 Guidelines for Good Clinical Practice) (from OHRP "Guidance on

Reviewing and Reporting Unanticipated Problems Involving Risks to Subjects or Others and Adverse Events (1/15/07)" http://www.hhs.gov/ohrp/policy/advevntguid.html#Q2).

An AE will be followed until it resolves or until 30 days after a participant terminates from the study, whichever comes first. Any change in clinical status, ECGs, routine labs, x-rays, physical examinations, etc., that is considered clinically significant by the study investigator is considered an AE. For the purposes of this protocol, consider a pregnancy an adverse event and follow the event until resolution of the pregnancy.

Suspected adverse reaction (SAR) is any adverse event for which there is a reasonable possibility that the drug caused the adverse event. For the purposes of safety reporting, 'reasonable possibility' means there is evidence to suggest a causal relationship between the drug and the adverse reaction. A suspected adverse reaction implies a lesser degree of certainty about causality than adverse reaction, which means any adverse event caused by a drug (21 CFR 312.32(a)).

Adverse reaction is any adverse event caused by the drug. Adverse reactions are a subset of all suspected adverse reactions for which there is reason to conclude that the drug caused the event.

7.2.2 Serious Events (Serious Adverse Events, Serious Suspected Adverse Reactions or Serious Adverse Reactions)

An AE or SAR is considered "serious" if, in the view of either the investigator or DAIT/NIAID/NIH it results in any of the following outcomes (21 CFR 312.32(a)):

- 1. Death: A death that occurs during the study or that comes to the attention of the investigator during the protocol-defined follow-up period must be reported whether it is considered treatment related or not.
- 2. A life-threatening event: An AE or SAR is considered "life-threatening" if, in the view of either the investigator or DAIT/NIAID/NIH, its occurrence places the subject at immediate risk of death. It does not include an AE or SAR that, had it occurred in a more severe form, might have caused death.
- 3. Inpatient hospitalization or prolongation of existing hospitalization.
- 4. Persistent or significant incapacity or substantial disruption of the ability to conduct normal life functions.
- 5. An important medical event that may not result in death, be life threatening, or require hospitalization may be considered an SAE when, based on appropriate medical judgment, it may jeopardize the participant and may require medical or surgical intervention to prevent one of the outcomes listed above.
- 6. Congenital anomaly or birth defect.

7.2.3 Unexpected Adverse Event

A SAR is considered "unexpected" when it is not listed in the Investigator Brochure at the specificity or severity that has been observed (21 CRF 312.32(a)).

7.3 Toxicity Grading

The study site assigns toxicity grades to indicate the severity of adverse experiences and toxicities. The CoFAR adopted usage of NCI-CTCAE v4.0 for application in adverse event reporting. We define allergic reactions in this protocol beyond the NCI-CTCAE system, and

further characterize anaphylaxis. Anaphylaxis is characterized as mild, moderate, or severe in Appendix 3, independent of the toxicity grade associated with the event. Toxicity grading for allergic reactions including anaphylaxis is modified from the NCI-CTCAE system to be more appropriate for this study population, and is displayed in Appendix 4. We reviewed the NCI-CTCAE v4.0 specifically for this protocol and it is otherwise appropriate for this study population. The purpose of using the NCI-CTCAE system is to provide standard language to describe toxicities and to facilitate tabulation and analysis of the data and assessment of the clinical significance of treatment-related toxicities.

The NCI-CTCAE provides a term and a grade that closely describes the adverse event. Each participating site received copies of the grading scales and event descriptions.

Record adverse events not included in the NCI-CTCAE listing and grade them 1 to 5 according to the General Grade Definition provided below:

Grade 1	Mild	Transient or mild discomforts (<48 hours), no or minimal medical intervention/therapy required, hospitalization not necessary (non-prescription or single-use prescription therapy may be employed to relieve symptoms, e.g., aspirin for simple headache, acetaminophen for post-surgical pain).
Grade 2	Moderate	Mild to moderate limitation in activity, some assistance may be needed; no or minimal intervention/therapy required, hospitalization possible.
Grade 3	Severe	Marked limitation in activity, some assistance usually required; medical intervention/therapy required, hospitalization possible.
Grade 4	Life-threatening	Extreme limitation in activity, significant assistance required; significant medical/therapy intervention required, hospitalization, or hospice care probable.
Grade 5	Death	Death

For additional information and a printable version of the NCI-CTCAE v. 4.03 manual, consult the NCI-CTCAE website, http://ctep.cancer.gov/reporting/ctc.html.

7.3.1 Guidelines for Determining Causality of an Adverse Event

The Investigator will use the following question when assessing causality of an adverse event to study drug: Is there a reasonable possibility that the drug caused the event?

An affirmative answer designates the event as a suspected adverse reaction.

The relationship, or attribution, of an adverse event to the study therapy regimen or study procedure(s) will initially be determined by the site investigator and recorded on the appropriate AE/SAE eCRF. Final determination of attribution for safety reporting will be determined by DAIT/NIAID/NIH. The relationship of an adverse event to study therapy regimen or procedures will be determined using the descriptors and definitions described previously.

For additional information and a printable version of the NCI-CTCAE manual, consult the NCI-CTCAE web site: http://ctep.cancer.gov/reporting/ctc.html.

7.4 Adverse Events Collection Procedures

Adverse events will be evaluated from the onset of the event until the time the event is resolved or medically stable, or until 30 days after the subject completes study treatment, whichever comes first.

AEs may be discovered through any of these methods:

- Observing the subject
- Questioning the subject, which should be done in an objective manner
- · Receiving an unsolicited complaint from the subject
- Review of medical records/source documents
- Review of home dosing symptom logs (provided to record symptoms between visits)

7.4.1 Recording and Reporting Procedures

Throughout the study, the investigator will record all AEs on the appropriate eCRF regardless of their severity or relation to study participation. A multi-page adverse event form will be used allowing all adverse events to be submitted through a single reporting mechanism. Serious adverse events will require additional information reported on additional pages within the EMMES AdvantageEDCSM system. Source documents can be scanned and attached to the adverse event form as well. The investigator will treat subjects experiencing adverse events appropriately and observe them at suitable intervals until their symptoms resolve or their status stabilizes.

